All study data are recorded in an electronic CRF with blinded data and identification via a study identification number. The study will apply to the specifications of act on processing of personal data. The database(e-CRF) is handled by REDCAP at Aarhus University, Aarhus, Denmark. Patient participation will be recorded in the medical record. Data will be stored at the Department of Neurology, Aarhus University Hospital, for 15 years, after which the documents will be shredded. Blood-samples in the research biobank will be stored until completion of the trial (no later than 31. january 2023).

Methodological experts from collaborators at Medical College Georgia, Augusta, USA ([name] and [name] lab) will remotely supervise the technical aspects of flowcytometry and ektacytometry and assist in the interpretation of results (only anonymized flowcytometry and ektacytometry data). Flowcytometry and ektacytometry results reflects only snapshots of the function and deformability of the red blood cells and change rapidly.

During the entire study period the local GCP unit will perform quality assurance control including source data verification. A complete list of all source data will be made and approved by the local GCP unit before study initiation. The investigator permits direct access to all source data/documents (including electronic patient record) at monitoring visits, audits and/or inspections by the regional ethics committee and Danish Medicines Agency.

9. Further documentation

- The study will respect and protect the patients' physical and mental integrity as well as their privacy. The data protection regulations as well as the law on data protection will abide.
- When the patient signs the consent form, the patient grants the study personnel access to information within the medical record necessary for the completion of the study. It also allows supervisory authorities in the Danish Medicines Agency access to the medical record in order to inspect and monitor the study. Information regarding previous admissions as

well as diagnoses are retrieved from national registers including the National Patient Registry, the Danish Stroke Registry and the Central Person Register.

- The study will be notified to the Region's Internal List of research projects
- The study is monitored by the GCP-unit Aalborg/Aarhus.
- The study is covered by the Danish Patient Compensation Association.

10. Economics

- Initiator: [name], Professor, [name], DMSc, Department of Neurology & Danish Stroke Center, Aarhus University Hospital.
- The ENOS trial has received funding from the Lundbeck Foundation on 140.000 dkr. (study investigator salary and current expenses)
- Equipment and supplies are supplied by the "mother trial", RESIST, which received funding from the following:
 - The Danish foundation Vilhelm Petersens mindelegat has supported the RESIST study with 1.240.000 dkr (research nurse salary and "stroke RIC" devices).
 - The Danish foundation TrygFonden has supported the RESIST study with 4.000.000 dkr (research personnel salaries, current expenses and investigational devices).
 - Aarhus University has supported the RESIST study with 550.000 dkr (RESIST study investigator salary)
 - Novo Nordisk has supported the RESIST study with 2.600.000 dkr (Rheo-erythrocrine dysfunction in stroke)
- Financial supporters have no influence on study design, data collection, analysis/interpretation of results or publication of results.
- The devices (Stroke-RIC and Sham-RIC) are produced by Seagull Aps. The company has no influence on study design, data collection, analysis/interpretation of results or publication of results.
- Financial contributions will be deposited into a fund account administered by Aarhus University Hospital's financial department. None of the physicians nor nurses involved in the study will benefit economically from their participation. Participation in the study is not linked to any remuneration.

11. Publication

Results, both positive, negative and inconclusive will be published in scientific papers and during scientific meetings/congresses.

12. Source data access and monitoring

Trial-related audits and/or monitoring will be provided by direct access to source data/documents. Local monitors from the Unit for Good Clinical Practice, Aarhus University, will perform the audit and monitoring. Before enrollment can start a trial monitoring plan must be available. The audit and monitoring process will involve a 100% monitoring of signed consent forms (“samtykkeerklæringer og fuldmagtserklæringer”) and serious adverse events.

[figure not shown]
13. Appendix

Appendix 1: Baseline data and treatment characteristics

Age	Platelet inhibitor treatment
Male/female	Anticoagulation therapy
Medical History	New oral anticoagulation treatment (NOAC)
Hypertension	Opioid treatment
Smoking	SSRI treatment
Alcohol	Clinical and physiological data
Hyperlipidemia	Modified Rankin Scale prestroke
Previous myocardial infarction Yes: within 3 months, yes: more than 3 months, no, unknown	NIHSS (Baseline)
Angina pectoris	Symptom onset (time)
Recent angina pectoris (< 4 weeks) If yes, date for latest episode	Time of admission
Atrial fibrillation	RIC compliance data
Previous ischemic stroke	
 • Time (start/stop) for each RIC/sham cycle • Bloodpressure and pulse at every RIC/sham RIC treatment
Stroke < 3 month If yes, date	
Previous TIA	NIHSS (7 days)
Recent TIA < 4 weeks If yes, date for latest episode	Stroke etiology (TOAST)
Previous ICH	Montreal Cognitive assessment at baseline-and +7 days
Peripheral artery disease	RIC questionnaire at +7 days
Physical activity (PASE interview)	IV tPA/EVT treated AIS
Medication on admission	Treatment initiation (time) and treatment characteristics
Statins	Quality indicators (Danish Stroke Registry)
Calcium channel blockers	
ACE inhibitors/angiotensin receptor blockers	
Beta-blockers	

Baseline data obtained from treating physician, database of Danish stroke center (ddsc.dk), Danish stroke registry and electronic health records.

Appendix 2: Study flowchart

Appendix 3: Montreal Cognitive Assessment

Montreal Cognitive Assessment (MOCA)

Navn: _____ Fødselsdag: _____ Køn: _____ Uddannelse: _____

VISUOSPATIEL / EKSEKUTIV		Kopier kuben					Tegn en urskive, der viser 10 min. over 11 (3 points)		
							Kontur [] Tal [] Visere []		
		[]	[]	[]	[]	[]	[]	___/5	
BENÆVNELSE									
		[]	[]	[]	[]	[]	[]	___/3	
HUKOMMELSE		ANSIGT FLØJL KIRKE IRIS RØD					Ingen point		
Læs ordliste: Patienten skal gentage dem. Lav 2 forsøg. Genfremkald efter 5 min.		1. forsøg							
		2. forsøg							
OPMÆRKSOMHED		Læs talrække (1 tal/sek.). Patienten skal gentage tal i samme rækkefølge. [] 2 1 8 5 4 Patienten skal gentage tal i omvendt rækkefølge. [] 7 4 2					___/2		
Læs bogstavlisten. Patienten skal banke i bordet med hånden, hver gang bogstav A læses. Ingen point ved > 2 fejl. [] F B A C M N A A J K L B A F A K D E A A A J A M O F A A B		___/1							
Seriel subtraktion med 7. Start med 100		[] 93	[] 86	[] 79	[] 72	[] 65	___/3		
		4-5 rigtige = 3 2-3 rigtige = 2 1 rigtig = 1 0 rigtig = 0							
SPROG		Gentag: Jeg ved kun, at det er John, der skal hjælpe i dag. [] Katten gemte sig altid under sofaen, når hundene var i stuen. []					___/2		
Ordmobilisering: Nævn alle de ord du kan på 1 minut, der begynder med bogstavet F [] _____ (N ≥ 11 ord)		___/1							
ABSTRAKTION		Ligheden mellem banan - appelsin = frugt [] tog - cykel [] ur - lineal					___/2		
FORSINKET GENKALDELSE		Genkaldelse uden hjælp ANSIGT [] FLØJL [] KIRKE [] IRIS [] RØD []						kun point for genkaldelse uden hjælp	___/5
Frivilligt Kategoriel hjælp choice									
ORIENTERING		DATO []	MDR. []	ÅR []	DAG []	STED []	BY []	___/6	
Normal ≥ 26/30		TOTAL _____/30 Tilføj 1 point hvis ≤ 12 års uddannelse							

EXE1590

© Z. Nasreddine MD, Version 7.0, www.mocatest.org. Dansk oversættelse: Kirsten Abelskov MD

[figure not shown]
Appendix 4: RIC questionnaire (Danish)

Example, minor changes may occur. Only patients with ischemic stroke.

REMOTE ISKÆMISK KONDITIONINGS SPØRGESKEMA

Patientens opfattelse af behandlingen

1. Hvor meget smerte/ubehag oplevede du under behandlingen (*afklemning af blodforsyningen til armen*)?
(Sæt kryds på nedenstående skala)

2. Har du under eller efter behandlingen (*afklemning af blodforsyningen til armen*) oplevet nogle bivirkninger til behandlingen?

JA, beskriv hvilke?: _____

NEJ

3. Såfremt *afklemning af blodforsyningen armen* kan beskytte mod udvikling af visse hjerte-kar sygdomme, ville du så være villig til at fortsætte med behandlingen efter at forsøget er færdigt?

JA

NEJ

4. Hvis du skulle fortsætte behandlingen i 1 år, hvor tit ville du være villig til at tage behandlingen?

2 gange dagligt

1 gang dagligt

Hver anden dag

- 2 gange om ugen
- 1 gang om ugen
- Mindre end 1 gang pr uge.

5. Hvor lang tid synes du hver behandling maksimalt måtte vare? (hver behandling varer nu 50 minutter)

- 1 time
- 50 minutter
- 40 minutter
- 30 minutter
- 20 minutter eller mindre

6. Man kan i forsøget du har været med i enten blive udtrukket til at blive behandlet med *én virksom* eller *én ikke-virksom* form af behandlingen. Hvilken for form af behandlingen blev du behandlet med?

- Den virksomme behandling
- Den ikke-virksomme behandling

Tak for din hjælp. Spørgeskemaet afleveres til forsøgspersonalet

14. References

1. Committee TEsoEcatEw. Guidelines for Management of Ischaemic Stroke and Transient Ischaemic Attack 2008 [cited 2017 3/8]. Available from: <https://www.karger.com/Article/Pdf/131083>.
2. Hjernesagen. Facts om hjerneskader [updated 28/4 2017; cited 2017 2/9 2017]. Available from: <https://www.hjernesagen.dk/om-hjerneskader/facts-om-hjerneskader>.
4. Pan JJ. Remote ischemic conditioning for acute ischemic stroke: dawn in the darkness. Reviews in the neurosciences. 2016;27(5):501-10.
5. Apopleksi DSf. Nationale retningslinjer for intravenøs trombolyselbehandling ved akut iskæmisk apopleksi Version 2. 2016. Available from: http://www.dsfa.dk/wp-content/uploads/Nationale_retningslinier_trombolyselbehandling_2016_110216.pdf.
6. Albers GW. Thrombectomy for Stroke at 6 to 16 Hours with Selection by Perfusion Imaging. The New England journal of medicine. 2018;378(8):708-18.

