A patient can withdraw from the study at any time. Withdrawal can also be due to the principal investigator's discretion. In case the patient cannot be reached by telephone, every effort will be made to contact the patient or to document the outcome regarding new vascular events via registries/electronic health records. If the patient withdraws from the study, the date and the reason for the patient's withdrawal will be recorded. The patient is encouraged to provide information about his or her reason(s) for withdrawal and any experienced adverse effects (AE) during the study.

The study will follow the course of the flow chart (please refer to appendix 2). A total of 45 patients will be included in the study: 15 will receive stroke-RIC, 15 will receive sham-RIC and 15 will constitute the control group. The initial RIC treatment regime will be applied as soon as possible and less than 48 hours after stroke onset. If patients are discharged from the Stroke Unit before day 7, they will continue the RIC treatment at home according to written instructions. On day 7 patients will return to the Stroke Unit for further tests (Table 2 – study procedures) and return the RIC device. The control group will consist of patients with putative stroke/TIA's ending up with a non-vascular diagnosis upon examination in the outpatient clinic or at the stroke unit. In addition to the study procedures all patients will receive standard treatment.

Method of blinding

Patients and the assessors of endpoints are blinded. No information regarding randomization status will be recorded in the patient record.

Discontinuation of study participation

A patient can withdraw from the study at any time. Patients can be withdrawn from the study at the principal investigator's discretion. If the patient withdraws from the study, the date and the reason for the patient's withdrawal will be recorded. The patient is encouraged to provide information about his or her reason(s) for withdrawal and any experienced adverse effects (AE) during the study.

Time schedule

The study is scheduled to start 1st of February 2020 and end upon 31st of January 2021. The inclusion period is scheduled to 5 months.

4. Study procedures and assessment

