If routine blood samples are taken, we will endeavor to include the baseline study blood samples in these in order to minimize discomfort for the patient. If, however, the routine blood samples cannot be drawn within less than 2 hours after inclusion, the study personnel will draw them. The blood samples will be safely stored at Aarhus University Hospital. No samples or biological material will be sent abroad. Research documents are stored for 15 years, after which they are destroyed

Blood samples	Accepted time frame
Baseline samples	< 2 hours from inclusion
+2-hour samples	1-3 hours from completed baseline RIC
+7 days samples	< 4 hours from completed 08 AM RIC

Intervention (Remote Ischemic Conditioning)

The investigational device used to induce RIC is an automatic Remote Ischemic Conditioning device (Stroke-RIC) – a blood pressure cuff for application on an upper arm. It is preprogrammed for 5 cycles of RIC. Each of these rounds consist of 5 minutes of inflation followed by 5 minutes of deflation. For the RIC device cuff pressure will be 200 mmHg unless the systolic blood pressure exceeds 175 mmHg in which case a pressure of 35mmHg will be added to the systolic pressure.

Patients allocated to the sham-RIC group will go through the same program as the intervention group, except the sham-RIC device cuff pressure will be only 20 mmHg during inflation.

The devices are designed and developed in corporation with Aarhus University, The faculty of Biomedicine technologies, 8200, Aarhus N, Denmark, Seagull Aps, 4160, Herlufmagle, Denmark and the department of Neurology, Aarhus University Hospital, 8000-DK, Aarhus C.

RIC/sham-RIC protocol	Accepted time frame
Baseline RIC	< 2 hours from inclusion
RIC twice daily for 7 days – 08.00 PM and AM	06.00 to 10.00 PM and 06.00 to 10.00 AM

RBC – deformability - Ectacytometry

The rheological properties of RBCs are quantified using a Deformability or Elongation Index (DI or EI). A higher EI at the optimum viscosity (300 Osmolality) indicates highly deformable RBCs indicative of better microcirculation, while a lower EI indicates rigid RBC's. Briefly, 6 uL of heparinized or EDTA treated fresh blood is mixed with 600-uL of polyvinylpyrrolidone (PVP) solution (300 Osm) and transferred to a disposable kit. The kit is placed inside the laser-assisted

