The following biochemical entities will be used (lab results performed as a part of standard operating procedure): C-reactive protein, Glucose, HBA1c, Potassium, Natrium, Calcium, Albumin, Creatinine, eGFR (estimated Glomerular Filtration Rate), Total WBC (White Blood Cell count/Leukocytes), Hemoglobin, Erythrocytes, Erythrocytes (Volume Fraction, EVF), Erythrocytes distribution widths (RDW), Erythrocyte median cell volume (MCV), Hemoglobin concentration (MCHC and MCH), Reticulocyte count, Platelet count, Iron, Transferring, Ferritin, International Normalized Ratio (INR), Activated Partial Tromboplastin Time (APTT), Cholesterol (Total, HDL, LDL, Triglyceride).

Montreal Cognitive Assessment (MoCA)

The Montreal Cognitive Assessment (MoCA) is a brief screening tool originally designed to identify mild cognitive impairment. MoCA is a 1-page (healthcare administered), 30-point test, administrable in \approx 10 minutes, which evaluates different domains: visuospatial abilities, executive functions, short-term memory recall, attention, concentration, working memory, language, and orientation to time and space (appendix 4).

PASE - physical activity in the elderly

Participants will be asked to complete the physical activity in the elderly (PASE) questionnaire during the acute hospital admission. PASE is a 12-item questionnaire, which quantifies the amount of PA over a 7-day period. The PASE questionnaire was developed with the purpose of assessing the level of PA in middle-aged and elderly individuals. The PASE score is calculated by taking the average number of hours spent on an activity (sports, occupational activity, household activities, and leisure time activities) per day over a 7-day period multiplied by an activity coefficient. Item scores are added to reveal the PASE score. The score may range from zero to more than 400.

Remote Ischemic Conditioning questionnaire

In the RIC questionnaire the study participants are asked to reveal the level of discomfort (if any) experienced during the investigational treatment and whether they knew which treatment they received (Sham/Sham-RIC) despite the blinded study design. Control subjects will not be interviewed with the RIC questionnaire. The questionnaire is administered by study personnel. (Appendix 4)

5. Statistical analysis

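### The RIC questionnaire calls the treatment arm occlusion before forcing an active/inactive guess, so the blinding check mixes knowledge, guessing and a cue of unknown direction

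*Protocol*

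**What the plan says.** - **Blinding claim.** Protocol section 3, Method of blinding: "Patients and the assessors of endpoints are blinded".
- **Purpose of the form.** Protocol section 4, Remote Ischemic Conditioning questionnaire: besides discomfort, patients are asked "whether they knew which treatment they received (Sham/Sham-RIC) despite the blinded study design". The bracket presumably means RIC/sham-RIC. The section adds: "The questionnaire is administered by study personnel". Table 2 places the form at day 7 only. The protocol describes no other check of patient blinding.
- **What the arms receive.** Protocol section 4, Intervention: the RIC cuff goes to 200 mmHg or above. The sham arm follows the same programme, "except the sham-RIC device cuff pressure will be only 20 mmHg during inflation".
- **The form.** Appendix 4 shows one version for all stroke patients, headed "Example, minor changes may occur. Only patients with ischemic stroke".
  - Items 1 and 2 ask about pain and side effects of the treatment, explained in brackets as "afklemning af blodforsyningen til armen" (clamping off the blood supply to the arm).
  - Item 3 repeats the description ("afklemning af blodforsyningen armen") and raises the possibility that it protects against some cardiovascular diseases.
  - Items 4 and 5 ask about willingness to continue and session length.
  - Item 6 explains that patients could be drawn to an active or an inactive form and asks "Hvilken for form af behandlingen blev du behandlet med". There are two boxes, active and inactive.

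**The concern.** Section 4 wants to learn whether patients knew their allocation. Item 6 records something else: a compulsory choice, made after the form has three times given a physical description of the treatment that fits one arm and not the other. A patient with no idea must still tick a box. A tick that comes from knowledge, from a guess or from the form's own wording looks the same.

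At stake is the trial's only described evidence on patient blinding. It matters most for the secondary endpoint on the difference in cognitive impairment at 7 days between treatment groups. That endpoint rests on the MoCA, a test the patient performs and whose result can depend on what the patient believes about the treatment.

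**Working it through.** The plan states no figure for this item, so there is nothing to reproduce. The check sets the form against its stated purpose and then asks what a two-box answer can and cannot show.

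**1. Purpose against instrument**

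| Needed for the purpose in section 4 | What Appendix 4 provides |
|---|---|
| Whether the patient knew | Which form the patient names |
| A way to say one does not know | Two boxes only |
| How sure, and on what grounds | Neither is asked |
| An answer not shaped by the form | Guess comes last, after items 1 to 3 describe occlusion |

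**2. What pure guessing gives.** Inputs: 15 RIC and 15 sham patients (section 3); chance of a correct guess 0.5 (assumption).
- Both arms: expected correct = 30 × 0.5 = 15. P(X ≥ 21) = 0.0214, so P(10 ≤ X ≤ 20) = 1 − 2 × 0.0214 ≈ 0.957.
- One arm of 15: P(X ≥ 11) = 0.059 and P(X ≥ 12) = 0.018, so 12 correct are needed for one-sided p < 0.05.
- Both arms of 15: P(X ≥ 20) = 0.049, so 20 of 30 are needed.
- With the 3 dropouts per arm that section 5 allows (12 per arm): 10 of 12 (p = 0.019; 9 gives 0.073), or 17 of 24 (p = 0.032; 16 gives 0.076).

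The item can therefore show a gross departure from chance at group level, and no more.

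**3. Why a correct tick is not knowledge.** Let k be the share who truly know and g the chance that anyone else ticks correctly. Then P(correct) = k + (1 − k)g. The values below are illustrative assumptions.
- k = 0.4, g = 0.5: 0.4 + 0.6 × 0.5 = 0.70.
- k = 0, g = 0.7 (wording favours the correct box): 0 + 1 × 0.7 = 0.70. This is the same result with nobody knowing.
- k = 0.4, g = 0.3 (wording favours the wrong box): 0.4 + 0.6 × 0.3 = 0.58. The same 40% who know are now partly hidden.

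**4. The direction of the cue is open.** A sham patient can reason in two ways:
- My cuff did not clamp anything, so I had the inactive form.
- The form tells me that my own treatment was clamping and might protect me, so I had the active form.

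The arm-specific index for a two-option guess is 2 × P(correct) − 1. If nobody knew and the cue moved sham answers of inactive from 50% to 80%, the index would be 2 × 0.8 − 1 = 0.6. If it moved them to 20%, the index would be 2 × 0.2 − 1 = −0.6. Both shifts are illustrative; the documents give no size. In an arm of 15, 80% is 0.8 × 15 = 12 correct, the threshold in step 2.

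**5. Why arms must be shown separately.** Suppose the cue moves RIC answers to 80% active.
- Sham answers 80% inactive: correct = 12 + 12 = 24 of 30 (80%), which looks like failed blinding.
- Sham answers 20% inactive: correct = 12 + 3 = 15 of 30 (50%), which looks like perfect blinding.

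**The case against.** The strongest reply is that a two-option guess, compared with 50% in each arm, is a usable blinding check. Forcing the choice also has a rationale: a don't-know box lets patients withhold a real suspicion, and it does not separate lucky guesses from knowledge among those who still choose. The protocol sets no rule equating a correct tick with knowledge, and the summary can be left to a SAP. All of this stands. A reader might infer that the form can neither support nor refute patient blinding; that goes too far, because the comparison by arm remains possible. A SAP can choose an index, however. It cannot remove a cue already given or recover a certainty that was never asked for.

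A reader might also infer that the form teaches sham patients what active treatment is and so overstates unblinding in that arm. The documents do not support this. Items 1 and 2 speak of the patient's own treatment, so the push could equally be towards active. Information is given orally and in writing at consent, that text is not shown, and by day 7 patients have used the device for about a week. The form may not be where they first meet the description. What remains is that non-neutral wording stands ahead of the guess.

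Finally, the form is labelled an example, and study personnel administer it, so an interviewer could note an unprompted don't-know. The label makes correction easy. But the text shown is the protocol's only specification of the form, and it has no field for such a note.

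**Conclusion.** The point holds as a minor one. As written, the questionnaire does not cleanly measure whether patients knew their treatment: the wording before item 6 is not neutral, and item 6 has no don't-know or certainty response. A comparison with 50% by arm survives but is confounded by the cue, and individual knowledge cannot be told from guessing.

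The direction and size of the cue's effect are unknown. The index range of −0.6 to 0.6 in the working shows only what an assumed 30-point shift would do in either direction. That there is a cue at all is an inference from the wording and the sham pressure.

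The reach is small. The form is used once, at day 7, so it cannot touch the baseline or +2-hour samples, and the laboratory primary endpoint is not affected. A weak blinding check does not itself bias the MoCA; it weakens the evidence that the MoCA comparison was made under blinding. The order of the form and the MoCA on day 7 is not stated.

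**What to change.** 1. In items 1 to 3, replace the occlusion wording with neutral text such as 'the cuff treatment'.
2. In item 6, add a don't-know option or a certainty rating, and ask for the main reason for the answer (for example pain, cuff pressure, perceived effect, told by someone).
3. Preferably ask the guess before any descriptive item.
4. Report the answers by arm, not only pooled.

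The cost is a small revision to a form that the protocol already leaves open to minor changes; visits, samples and sample size stay as they are. There are two downsides. A don't-know box loses information if patients use it to withhold a suspicion, which a forced choice with a certainty rating avoids. Asking the guess first may influence the discomfort rating that follows. If that is judged the greater risk, keep item 6 last and rely on the neutral wording.
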